7.2	STATISTICAL METHODS	19
7.3	SUBJECT POPULATION(S) FOR ANALYSIS	19
8	SAFETY AND ADVERSE EVENTS	20
8.1	DEFINITIONS.....	20
8.2	RECORDING OF ADVERSE EVENTS.....	21
8.3	REPORTING OF SERIOUS ADVERSE EVENTS AND UNANTICIPATED PROBLEMS	22
8.3.1	Sponsor-Investigator reporting: notifying the Mayo IRB	22
8.3.2	Sponsor-Investigator reporting: Notifying the FDA	23
8.4	UNMASKING/UNBLINDING PROCEDURES	23
8.5	STOPPING RULES.....	23
8.6	MEDICAL MONITORING	23
9	DATA HANDLING AND RECORD KEEPING	23
9.1	CONFIDENTIALITY	23
9.2	SOURCE DOCUMENTS	24
9.3	CASE REPORT FORMS	24
9.4	RECORDS RETENTION	25
10	STUDY MONITORING, AUDITING, AND INSPECTING	25
10.1	STUDY MONITORING PLAN	25
10.2	AUDITING AND INSPECTING	26
11	ETHICAL CONSIDERATIONS	26
12	STUDY FINANCES	26
12.1	FUNDING SOURCE	26
12.2	CONFLICT OF INTEREST	26
12.3	SUBJECT STIPENDS OR PAYMENTS	27
13	PUBLICATION PLAN	27
14	REFERENCES	27
15	ATTACHMENTS	28

List of Abbreviations

LIST OF ABBREVIATIONS

AE	Adverse Event/Adverse Experience
CFR	Code of Federal Regulations
CRF	Case Report Form
CSU	Chronic Spontaneous Urticaria
DSMB	Data and Safety Monitoring Board
FDA	Food and Drug Administration
GCP	Good Clinical Practice
HIPAA	Health Insurance Portability and Accountability Act
IB	Investigator's Brochure
IND	Investigational New Drug Application
IRB	Institutional Review Board
PHI	Protected Health Information
PI	Principal Investigator
SAE	Serious Adverse Event/Serious Adverse Experience
SOP	Standard Operating Procedure
UAS	Urticaria Activity Score
UCT	Urticaria Control Test

Study Summary

Title	Mepolizumab for the Treatment of Chronic Spontaneous Urticaria: An Open-Label, Single-Arm, Exploratory Study
Running Title	Mepolizumab (Nucala) for the Treatment of Chronic Spontaneous Urticaria
Protocol Number	17-009322
Phase	Investigational Exploratory Trial
Methodology	Single arm, Open-label, Exploratory Trial
Overall Study Duration	13 months (10 month accrual period)
Subject Participation Duration	12 weeks
Single or Multi-Site	Mayo Clinic Florida
Objectives	To investigate the potential efficacy of mepolizumab (Nucala) in the treatment of biopsy proven chronic spontaneous urticaria
Number of Subjects	20
Diagnosis and Main Inclusion Criteria	
Main inclusion criteria:
 
18 years old or older at time of consent with history and physical exam consistent with CSU, lasting greater than 6 weeks and unresponsive to oral antihistamines

Study Product, Dose, Route, Regimen	Mepolizumab (Nucala) 200 mg SQ every 2 weeks x 10 weeks
Duration of Administration	10 weeks
Reference therapy	None

Statistical Methodology	
This is an exploratory study designed to generate preliminary data in evaluating the efficacy of mepolizumab (Nucala) in the treatment of CSU. The primary outcome measure is derived from the UAS7 used to quantify number of hives and daily pruritus.
 
A paired t-test will be used to evaluate mean differences before and after treatment at a $p=0.05$ significance level. The primary endpoint of the study is the UAS7. A 10 point change in the UAS7 has been reported to be the minimal clinically significant difference in therapeutic trials for urticaria. The study is powered at 99% to detect a 10 point change in the UAS7 at a 5% significant level with the proposed accrual target of 20 patients.

-------------------------	---

1. Introduction

This document is a protocol for a human research study. This study will be carried out in accordance with the protocol, Good Clinical Practice standards, and applicable United States government regulations and Mayo Clinic research policies and procedures.

1.1 Background

Chronic spontaneous urticaria (CSU) is a common skin disorder affecting 0.1 to 1% of the general population and is characterized by recurrent, transitory, pruritic erythematous plaques present for a minimum of 6 weeks. In 30 to 50% of CU cases, there is an autoimmune etiology with autoantibodies against IgE, Fc ϵ RI or Fc ϵ RII (CD23). These autoantibodies are postulated to bind to the surface of mast cells and basophils initiating a signal transduction cascade resulting in the secretion of histamine and other inflammatory mediators which produce the observed clinical features of edema, erythema, and localized pruritus. The impact of CSU on quality of life is quite significant with most cases lasting an average of 3 to 5 years.

1.2 Investigational Agent

Mepolizumab (Nucala) is a human interleukin-5 antagonist indicated for add-on maintenance treatment of patients with severe asthma with an eosinophilic phenotype. For this study, it will be supplied as a 100 mg lyophilized powder for reconstitution to be administered subcutaneously by trained study personnel.

1.3 Preclinical Data

Interleukin-5 has been previously established to stimulate proliferation and maturation of eosinophils. Eosinophils release major basic protein (MBP) which induces mast cell and basophil degranulation [1,3]

1.4 Clinical Data to Date

Since more than half of the patients with CSU do not show evidence of auto-Abs either against the high-affinity IgE receptor or against IgE Ab, additional therapeutic approaches are needed. An alternative pathway for allergen-independent histamine release by basophils and mast cells is through major basic protein (MBP) released by eosinophils. Incubation of human basophils and mast cells with MBP results in a non-cytotoxic, dose-dependent histamine release from target cells within 30 min. Additionally, IgE binding to the low-affinity IgE receptor (Fc ϵ RII/CD23) on eosinophils also results in eosinophilic activation and MBP release.

Therefore, we hypothesize the IL-5 neutralizing properties of mepolizumab (Nucala) on eosinophil maturation and function may have therapeutic utility in the management of CSU. Support for the

relevance of these mechanisms in the pathogenesis in CSU is reflected by the accumulation of interstitial and perivascular dermal eosinophils in lesional skin biopsies. Elevated levels of IL-5 mRNA expression have also been demonstrated from both eosinophilic and lymphocytic components of the inflammatory infiltrate.

1.5 Dose Rationale

The dosing of mepolizumab (Nucala) in this study will be 200 mg SQ administered at weeks 0,2,4,6 and 8. We are aware of prior investigations establishing that monthly doses of Nucala are effective in reducing peripheral eosinophilia and that higher and more frequent dosing are not associated with a longer or more sustained clinical response in reducing asthma exacerbations. We are also aware of prior studies where a 300 mg monthly SQ dose has been safe and effective in treating Eosinophilic Granulomatous Polyangiitis and Hypereosinophilic Syndrome. The concern in this study is with respect to what is the minimum effective dose that reduces peripheral eosinophilia and is also sufficiently inhibitory to prevent pathologic eosinophilic accumulation in lesional skin in response to an acute inflammatory signal. We reviewed early published reports of IV Nucala at 750 mg in atopic dermatitis that failed to demonstrate efficacy and the authors raised the possibility that more frequent administration may have been helpful. Although the mechanism of eosinophilic recruitment into the skin in atopic dermatitis and chronic urticaria differs, existing data does suggest more frequent dosing can be beneficial for skin disorders especially given the nature of the inflammatory cascade in chronic urticaria. As this is a proof of concept study and the safety profile of Nucala has been established to be extremely robust, we felt to error on the side of more frequent administration to avoid missing a potential therapeutic effect. We are open to considering a monthly 300 mg SQ dose, if there are significant safety concerns with the proposed dosing interval of 200 mg SQ q2 weeks.

1.6 Risks and Benefits

The postulated benefits of Nucala include sustained immunomodulatory effects resulting in improvement of pruritus and clearance of lesional skin without the direct end organ toxicities seen

The following risks of Nucala are felt to be low and manageable with the study protocol and do not outweigh the aforementioned benefits:

1. Hypersensitivity Reactions

Anaphylaxis has occurred following administration of Nucala. This risk is idiosyncratic and will be minimized by administrating Nucala in a supervised medical setting and requiring study participants to carry epinephrine autoinjectors at all times.

2. Acute Asthma Symptoms or Deteriorating Disease

Nucala is not indicated for the treatment of acute asthma symptoms or acute exacerbations. This risk will be minimized by screening all study participants with asthma via the asthma control test (ACT) questionnaire and peak flow measures at each visit. Those with ACT scores less than 20 and/or peak flow measures greater than 10% below their personal best will not receive the study drug on the day of their visit. Subjects with severe asthma (requiring high-dose inhaled or systemic corticosteroids) will be excluded from the study.

3. Opportunistic Infections: Herpes Zoster

In controlled clinical trials, two serious adverse reactions of herpes zoster occurred in subjects treated with Nucala compared with none in placebo. The mechanism by which this adverse reaction occurs is unclear. Subjects will be monitored for signs and symptoms of shingles and treated should shingles develop.

4. Reduction of Corticosteroid Dosage

Reductions in corticosteroid dose, if appropriate, will be gradual and performed under the direct supervision of a physician.

5. Parasitic (Helminth) Infection

Eosinophils may be involved in the immunological response to some helminth infections. Patients with known parasitic infections were excluded from participation in clinical trials. It is unknown if Nucala will influence a patient's response against parasitic infections. This risk will be minimized by excluding enrollment of study participants with known tapeworm or roundworm infections.

2 Study Objectives

The primary objective of this study is to investigate the potential efficacy of mepolizumab in the treatment of biopsy proven chronic spontaneous urticaria. The primary measurement of efficacy will be the mean reduction in the seven day urticaria activity score (UAS7) before and after 10 weeks of treatment with mepolizumab. Secondary measure of efficacy will be the mean reduction of the urticaria control test (UCT) score and the weekly itch severity score (ISS) before and after treatment.

3 Study Design

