5.2 Exclusion Criteria

Patients are to be excluded based on the following criteria:

- Vulnerable study population
- If you are female and pregnant
- Biopsy proven neutrophilic rich urticarial which is unlikely to respond to mepolizumab given the postulated therapeutic mechanism
- Known history of adverse reaction to mepolizumab (Nucala)

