6.2 Treatment Regimen

All study participants will receive Nucala 200 mg SQ at week 0, 2,4,6, and 8 for a total of 5 injections.

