7.3 Visit 3 (Week 2± 5 days)

- a) UAS7 score assessment
- b) ISS score assessment
- c) Nucala 200mg injection
- d) Screen for adverse events

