7.6 Visit 7 (week 10± 5 days)

- a) UAS7 score assessment
- b) ISS score assessment
- c) UCT score assessment
- d) 4mm punch skin biopsy if residual disease
- e) Collect UAS log book
- f) Blood work: CBC with differential, serum IgE level, chronic urticaria index, IgE Fc receptor antibody functional assay
- g) Screen for adverse events
- h) Photograph biopsy site

Week	Wk -2 screen	Wk 0 baseline	Wk 2	Wk 4	Wk 6	Wk 8	Wk 10
Visit	1	2	3	4	5	6	7
Consent/Enroll	X						
Distribute log book	X						
Collect log book							X
Cbc with Diff	X						X
Serum IgE	X						X
CIU index	X						X
IgE Fc Recept Ab	X						X
Urine HCG	X						
UCT		X					X
UAS		X	X	X	X	X	X
ISS		X	X	X	X	X	X
Skin Biopsy	X						X***
Nucala Inj*		X	X	X	X	X	
Cetirizine (Zyrtec) Dispense	X						
Epinephrine auto-injector Dispense		X					
AE Screening**		X	X	X	X	X	X
	
* Nucala Inj = denotes Nucala SQ injection during a visit ** AE Screening = protocol directed screening for adverse events ***At end of study if subjects have residual disease, will biopsy, as necessary, to check for lesional eosinophil tissue density
						

8 Statistical Plan

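### The asthma and worm-infection safeguards promised in section 1.6 are missing from the eligibility, dosing, visit and source-data sections

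*Combined protocol and SAP*

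**What the plan says.** Section 1.6 (Risks and Benefits) describes the risks of the drug as low and manageable under the protocol and gives the measures that make them so. Item 2, on asthma, contains three:

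- an exclusion: "Subjects with severe asthma (requiring high-dose inhaled or systemic corticosteroids) will be excluded from the study";
- a check: "screening all study participants with asthma via the asthma control test (ACT) questionnaire and peak flow measures at each visit";
- a dosing limit, applied on the day of the visit: "Those with ACT scores less than 20 and/or peak flow measures greater than 10% below their personal best will not receive the study drug".

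Item 5 adds a second exclusion. The helminth risk is to be reduced by "excluding enrollment of study participants with known tapeworm or roundworm infections".

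Section 5.2 opens with "Patients are to be excluded based on the following criteria" and gives four bullets: vulnerable population, pregnancy, neutrophil-rich urticaria on biopsy, and a previous adverse reaction to mepolizumab. Section 6.2 states: "All study participants will receive Nucala 200 mg SQ at week 0, 2,4,6, and 8 for a total of 5 injections". The dosing-visit lists in Section 7 (Visits 2 to 6) contain the UAS7, the itch severity score and the injection. Visits 3 to 6 add "Screen for adverse events"; Visit 2 has the epinephrine auto-injector in that position. The nearest entry in the schedule table is explained as "AE Screening = protocol directed screening for adverse events".

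**The concern.** Section 1.6 is a risk discussion. Staff screen from the eligibility lists, dose from the treatment section and run visits from Section 7 and the schedule table. A rule that appears only in 1.6 depends on someone remembering to go back to it.

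Two things are at stake. First, a patient with severe asthma or a known worm infection could pass every listed criterion and be enrolled, although 1.6 bars that patient. Second, a participant with asthma could be dosed on a day when 1.6 requires the dose to be withheld, because no visit produces the ACT score, the peak flow or the personal best that the limit needs. In the other direction, staff who do withhold a dose depart from 6.2 as written and have no instruction on what to do next.

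This is a matter of participant safety and of whether the protocol can be carried out as written. It is not a claim about bias in the UAS7 result.

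**Working it through.** The plan states no figure on this point, so the check sets 1.6 against each operating section and counts.

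| Safeguard in 1.6 | Where it should reappear | What is there |
|---|---|---|
| Severe asthma excluded | 5.1 (6 bullets), 5.2 (4 bullets) | Named in 0 of 6 + 4 = 10 |
| Known worm infection excluded | 5.1, 5.2 | Named in 0 of 10 |
| ACT and peak flow at each visit (asthma) | Visits 1 to 7 | 0 of 7 lists |
| Same | Schedule table | 0 of 16 procedure rows |
| Same | 4.5 (5 CRF items + 2 supportive items) | 0 of 7 |
| Personal-best peak flow (needed for the limit) | Visit 1 or elsewhere | Not obtained at any visit |
| Dose withheld on ACT or peak flow | 6.2 | No condition stated |

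The three zeros for ACT and peak flow are one omission seen in three places, not three defects. The lists and the table are intact in the text, so the gap does not come from redaction or from reading the PDF.

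**Is this simply how the protocol is drafted?** No. The 1.6 safeguard against anaphylaxis, the epinephrine auto-injector, is repeated in 6.6, in the Visit 2 list and in its own schedule row. The asthma and worm safeguards were not carried over in the same way.

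**What partial cover exists?**

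- *Eligibility.* One of the 10 criteria, good general health on medical history (5.1), could keep such a patient out by judgement. The history and physical at Visit 1 could reveal either condition. Neither names them.
- *Dosing.* Adverse-event screening is listed at 4 of the 5 dosing visits (Visits 3 to 6), and the schedule table also marks week 0, making 5 of 5. Section 9.1 treats worsening of a preexisting condition as an adverse event, and 9.2 calls for specific questioning. A flare could therefore be noticed. In all 4 lists, however, the screen is item d and the injection item c. List order may not be the order of conduct, so little weight rests on this. The main point is that the screen does not produce the numbers the limit uses.
- *Discontinuation.* The adverse-event reason in 5.4.1 concerns leaving the study, not holding one dose.

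**What follows a withheld dose?** The visit window is ±5 days. If the visit falls d days from the nominal date, 5 − d days remain: 10 for d = −5, 5 for d = 0, and 0 for d = +5. Whether the dose can be given later within the window depends on when the visit took place, so the protocol has to say whether it is delayed or skipped. This is a secondary point.

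**The case against.** The counts are not disputable, so the case on the other side concerns weight.

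- **Section 5.2 is silent; it does not contradict 1.6.** Section 1.6 is part of the same protocol, its wording is mandatory, and both sections can be obeyed together. This is fair as far as it goes: a reader of the whole document finds the rules. But an exclusion list that leaves out two exclusions gives a different answer on who is eligible from the one 1.6 gives.
- **Section 6.2 is shorthand for the nominal regimen.** It also leaves out the confirmatory-biopsy condition in 3.1. That is so, and it explains the wording. It does not put the limit anywhere else in the dosing instructions.
- **There is more cover than first appears.** Section 3.1 requires a standardized history and examination, and 5.4.1 allows withdrawal of someone who should not have been enrolled. Both exclusions are history items that need no extra procedure. This stands for the exclusions, although the first is not directed at either condition and the second acts after enrolment. It does nothing for the ACT and peak-flow limit.
- **Some material is not visible.** The consent form, which 5.3 says describes the criteria, and the CRF are not available. Section 3.1 mentions an attached summary, while section 16 lists no attachments. This stands: it cannot be said that staff lacked the rules, only that the operating sections omit them.
- **The harm is hypothetical.** Mepolizumab is itself indicated for severe eosinophilic asthma (1.2), and 1.6 says only that it is not a treatment for acute symptoms or exacerbations. This limits the likely consequence of a missed exclusion. It does not remove a commitment on which the protocol's own risk judgement rests.

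**Conclusion.** The concern holds and should be fixed. Two exclusions and one dose-withholding limit stated in 1.6 are absent from the sections that govern eligibility, dosing, visits and source data. None of the 10 criteria names either exclusion, and no visit obtains the values the limit requires. The remaining cover is discretionary and does not apply the numeric limit before a dose.

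The conclusion rests on the text alone. It assumes that staff may work from 5.2, 6.2 and Section 7 without returning to 1.6; training, worksheets and the CRF could have closed the gap in practice and cannot be checked. The number of participants with asthma or a known worm infection is not given and may be zero among the 20, so no count of affected patients is offered.

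**What to change.** 1. Add severe asthma (with the definition in 1.6) and known tapeworm or roundworm infection to 5.2.
2. For participants with asthma, record personal-best peak flow at Visit 1. Add ACT and peak flow at Visits 1 to 7, taken before the injection at Visits 2 to 6, to the Section 7 lists, the schedule table and 4.5. If only Visits 2 to 6 are intended, change 1.6 to refer to dosing visits.
3. Make the regimen in 6.2 subject to the 1.6 limits.
4. State whether a withheld dose is skipped or given later within the ±5-day window, and add a CRF field for a withheld dose and its reason.

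The cost is amendment wording, a few CRF fields, and a short questionnaire and peak-flow reading for participants with asthma, both of which 1.6 already promises.

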3.1 General Description

This is an open-label, single arm exploratory study of mepolizumab in the treatment of CSU. The primary endpoint will be the mean reduction in the seven day urticaria activity score (UAS7) before and after 10 weeks of treatment with mepolizumab. Secondary endpoints will be the mean

reduction of the urticaria control test (UCT) score and the weekly itch severity score (ISS) before and after treatment. Enrollment examination will include a standardized history and examination, baseline UCT score, CBC with differential, serum IgE level, chronic urticaria index, IgE Fc receptor antibody functional assay, and a 4 mm punch biopsy of lesional skin. Patients will discontinue all anti-histamines and start cetirizine 10 mg PO BID which will be continued throughout the study duration. Patients will be provided with a log book to track daily urticaria signs and symptoms in a standardized manner for UAS scoring. At week 0 (enrollment visit +7 days), baseline UAS7 and ISS score will be assessed and skin biopsy results reviewed. Patients with a confirmatory skin biopsy will receive 200 mg SC of mepolizumab at week 0,2,4,6, and 8. UAS-7 and weekly ISS score will be calculated at week 0, 4, 8, and 10. UCT scoring will be calculated at week 0 and at week 10. Repeat CBC with differential, serum IgE level, and measures of basophil serum activation (chronic urticaria index, IgE FC Receptor antibody functional assay) will be assessed at week 10. Attached to this document is a protocol summary.

4 Number of Subjects

Twenty

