7.1 Visit 1 (Week -2/Screening & Enrollment)

- a) Informed Consent
- b) History & Physical
- c) 4 mm punch skin biopsy (**4 mm punch skin biopsy within 6 months prior to visit 1 is acceptable**)
- d) UCT score assessment
- e) Review and distribute UAS log book
- f) Blood work: CBC with differential, serum IgE level, chronic urticaria index, IgE Fc receptor antibody functional assay (**Blood work within 6 months prior to visit 1 is acceptable**)
- g) Urine Pregnancy Test (if applicable)
- h) Photograph Biopsy site (**Photograph Biopsy site within 6 months prior to visit 1 is acceptable**)
- i) Dispense cetirizine (Zyrtec) 10 mg PO BID (#140 tablets)

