7.2 Visit 2 (Week 0± 5 days Baseline)

- a) UAS7 score assessment
- b) ISS score assessment
- c) Nucala 200mg injection
- d) Dispense epinephrine auto-injector

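### The baseline UCT visit is contradictory: week -2 in the visit lists, week 0 in the schedule table, and both in Section 3.1

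*Combined protocol and SAP*

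**What the plan says.** Section 4.3 makes the mean change in UCT over 10 weeks of treatment a secondary endpoint, and Section 8.1 plans paired t-tests of before/after differences. The pre-treatment UCT is placed as follows.

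- **Section 3.1, enrollment:** "Enrollment examination will include a standardized history and examination, baseline UCT score".
- **Section 3.1, scoring times:** "UCT scoring will be calculated at week 0 and at week 10". The same paragraph makes week 0 a separate, later visit and names only the other two scores as baseline there: "At week 0 (enrollment visit +7 days), baseline UAS7 and ISS score will be assessed".
- **Section 7.1 (Visit 1, week -2):** "d) UCT score assessment". Item i of the same list reads "Dispense cetirizine (Zyrtec) 10 mg PO BID".
- **Section 7.2:** the heading is "7.2 Visit 2 (Week 0± 5 days Baseline", and the list holds UAS7, ISS, the injection and the epinephrine auto-injector, with no UCT.
- **Section 7.6 (Visit 7, week 10):** "c) UCT score assessment". This is the only other UCT in the visit lists.
- **Schedule table at the end of Section 7:** UCT is blank at week -2 and marked at week 0 and week 10 only.

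On background treatment, Section 3.1 says "Patients will discontinue all anti-histamines and start cetirizine 10 mg PO BID which will be continued throughout the study duration". Section 6.6 has cetirizine start two weeks before the first mepolizumab dose.

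**The concern.** In a single-arm before/after comparison, the baseline visit defines what is estimated. Here the two candidate visits lie on either side of a change in background antihistamine treatment. A change measured from Visit 1 combines that switch with mepolizumab. A change measured from week 0 starts after the switch, at the same visit as the UAS7 and ISS baselines in every part of the protocol.

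There is also a data-collection risk. Staff working from the Section 7 lists would collect no week 0 UCT, and a missed score cannot be recovered later. Staff working from the table would collect no week -2 UCT. If different patients were handled differently, the paired analysis would mix two kinds of change score.

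**Working it through.** **Step 1: set the sources side by side.**

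| Source | UCT at week -2 / enrollment | UCT at week 0 | UCT at week 10 |
|---|---|---|---|
| Section 3.1, enrollment sentence | yes, called baseline | – | – |
| Section 3.1, scoring sentence | not listed | yes | yes |
| Visit lists 7.1, 7.2, 7.6 | yes | no | yes |
| Schedule table | no | yes | yes |

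The sources agree on week 10. The lists and the table exclude each other on the pre-treatment visit, and Section 3.1 supports each of them once.

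**Step 2: rule out a table-reading error.** In the table, the UCT row has the same leading offset as the UAS and ISS rows, whose first mark is at week 0. Rows marked at week -2, such as consent and CBC, are offset differently. The scoring sentence in Section 3.1 supports week 0 independently.

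**Step 3: ask whether two pre-treatment UCTs were intended.** Section 3.1 alone could be read that way. The other sources do not support it: list 7.2 omits the week 0 score, the table omits the week -2 score, and nothing says which would enter the paired test.

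**Step 4: illustrate the possible size.** The documents give no SD for UCT change and no estimate of a switch effect, so both are assumed here.

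- From the protocol: n = 20, paired t-test, 5% level (taken as two-sided), UCT range 0 to 16.
- Assumed: SD of change 3, 4 or 5 points; no mepolizumab effect; a mean shift of 0.25, 0.5 or 1 point from the switch alone, lasting to week 10.

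With 19 degrees of freedom the critical value is t = 2.093. The smallest significant mean change is 2.093 × SD / √20, which is 1.40, 1.87 and 2.34 points for SD 3, 4 and 5.

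The probability of p<0.05 comes from the noncentral t distribution with noncentrality shift × √20 / SD. For example, a 1-point shift with SD 3 gives 1 × 4.472 / 3 = 1.491 and a probability of 0.294.

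| Switch-only shift | SD 3 | SD 4 | SD 5 |
|---|---|---|---|
| 0 | 0.050 | 0.050 | 0.050 |
| 0.25 point | 0.064 | 0.058 | 0.055 |
| 0.5 point | 0.109 | 0.083 | 0.071 |
| 1 point | 0.294 | 0.186 | 0.136 |

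The test is two-sided, so a negative shift gives the same probabilities. A real mepolizumab effect could then be hidden rather than inflated.

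**The case against.** - **The intent can largely be recovered.** The scoring sentence in Section 3.1 and the table both say week 0. List 7.2 also omits the adverse-event screening that the table marks at week 0, so the missing UCT may be a drafting slip. This is plausible, but item d of 7.1 and the enrollment sentence in 3.1 positively place a UCT at enrollment, so the text still needs correction.
- **Only week 0 is called the baseline visit.** That is true of the visit headings and the table. Section 3.1 nevertheless calls the enrollment score baseline.
- **The switch may affect few patients.** Section 3.1 stops all antihistamines, whereas Section 6.6 mentions only other first-generation ones; those two passages must be reconciled. Entrants are also unresponsive to antihistamines (Section 5.1), so any shift could be small. This stands and limits the likely size.
- **Week 0 may not be fully clean.** Section 4.3 describes UCT as retrospective and gives no recall period. The run-in is 7 days in Section 3.1 but two weeks in Sections 6.6 and 7.1, with a ±5-day window at Visit 2. If recall exceeds the run-in, a week 0 score still covers some time before cetirizine. This also stands: week 0 is the better baseline, but it does not guarantee isolation of the drug effect.
- **The 5% reference is idealised.** Regression to the mean, expectation and natural course can move UCT from either baseline in an open-label single-arm study. The table above isolates the switch only.
- **The stakes are limited.** UCT is secondary in a 20-patient exploratory study. That is correct, and it bears on priority rather than on whether the contradiction exists.

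**Conclusion.** The concern holds. The protocol is wrong as written on this point, because its visit lists and its schedule table give incompatible visits for the baseline of a named secondary endpoint. This finding rests on the text alone and needs no assumption.

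The numerical effect is unknown. Under the assumed SDs and a persistent shift, it is negligible if the switch barely moves UCT (5.5% to 6.4% at 0.25 point), modest at 0.5 point (7% to 11%) and material at 1 point (14% to 29%). The primary UAS7 analysis and its stated power do not depend on the choice of UCT visit. The correction should be made, but the primary result is not at risk.

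**What to change.** 1. State that the analysis baseline for UCT is the week 0 score (Visit 2), completed before the injection, as the table and the scoring sentence in Section 3.1 already indicate.
2. Add UCT to list 7.2 ahead of item c.
3. Remove the Visit 1 UCT from 7.1, or label it screening only and mark it so in the week -2 column of the table.
4. Delete the word baseline from the enrollment UCT in Section 3.1.
5. Check that the case report form records UCT under the same visit labels, since Section 4.5 has UCT entered there directly.
6. State the UCT recall period, so that readers can judge how far the week 0 score reflects time on cetirizine.

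The cost is a wording amendment to Sections 3.1, 7.1 and 7.2 (and the table if a screening UCT is kept), submitted to the IRB under Section 12, with a case report form change if the form follows the visit lists. No visit is added. Moving the questionnaire keeps two administrations per patient; keeping a screening UCT as well makes three.
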